18.3. Patient Termination

A study patient will be terminated if the study patient develops any severe adverse event that may be related to the study. A study patient will receive appropriate treatment at the discretion of the investigator. Notification of termination will be clearly documented. These study patients are considered to have completed the study and will not be replaced.

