7.3. Exclusion Criteria

If any of the following exclusion criteria are applicable to the subject or either eye, the subject should not be enrolled in the study.

- Subjects with history of previous ocular surgery.
- Subjects with topographic evidence of keratoconus, or ectasia.
- Subjects with autoimmune diseases.
- Subjects who are pregnant or nursing.
- Systemic disease likely to affect wound healing, such as diabetes and severe atopy.
- Any ocular disease (including un-controlled dry eye) which in the investigator's opinion would affect the outcome of refractive surgery.

The principal investigator reserves the right to declare a patient ineligible or nonevaluable based on medical evidence that indicates they are unsuitable for the trial.

Pregnancy has a known effect on the stability of refractions and visual acuity. As such, subjects who become pregnant during the study will not be discontinued but their data may be excluded from analyses of effectiveness.

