9.2.2. Operative (Surgery)

All subjects will undergo bilateral LASIK surgery. The surgeon's usual standard of care with regard to treatment and medication will be used for all study subjects. Surgery planning will be performed using the surgeon's preferred method.

Any adverse events/serious adverse events (AEs/ SAEs) occurring during surgery will be noted at this visit. Any other problems during surgery and comments regarding surgery will be documented.

Any subject whose surgery is not completed successfully will be documented in the appropriate case report form. These subjects will be monitored for safety but clinical performance data may be excluded from the analysis.

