12.3.1 Intensity and Causality Assessments

For every adverse event and quality complaint, the investigator must assess the causality as Related or Not Related to the medical device under investigation. An assessment of causality will also be performed by the Medical Monitor utilizing the same definitions, as shown below:

Causality

- Related An adverse event or quality complaint classified as related may be either definitely related or possibly related where a direct cause and effect relationship with the medical device has not been demonstrated, but there is a reasonable possibility that the adverse event or quality complaint was caused by the medical device.
- Not Related An adverse event or quality complaint classified as not related may either be definitely unrelated or simply unlikely to be related (i.e., there are other more likely causes for the adverse event or quality complaint).

Where appropriate, the investigator must assess the intensity (severity) of the adverse event as mild, moderate, or severe based on medical judgment with consideration of any subjective symptom(s), as defined below:

Intensity (Severity)

vent is mild if the subject is aware of but can easily
ign or symptom.
vent is moderate if the sign or symptom results in
gnificant enough to cause interference with the
al activities.
vent is severe if the sign or symptom is incapacitating the subject's inability to work or engage in their es.

The investigator must document any action taken (i.e., medication, intervention, or treatment plan) and outcome of the adverse event or quality complaint when applicable.

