13.4. Follow-Up of Adverse Events and Quality Complaints

The investigator is responsible for adequate and safe medical care of subjects during the study and for ensuring that appropriate medical care and relevant follow-up procedures are maintained after the study. Any additional data from these follow-up procedures must be documented and available to the study coordinator who, with the Medical Monitor, will determine when the data need to be documented on the CRFs.

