13.5. Safety Analyses

The type, severity, duration and frequency of reported ocular adverse events will be tabulated. Adverse events will also be summarized for events that were considered treatment-related.

14. GCP, ICH and ETHICAL CONSIDERATIONS

This study will be conducted in compliance with Good Clinical Practices (GCPs), including International Harmonization (ICH) Guidelines, and in general, consistent with the 1996 version of the Declaration of Helsinki. In addition, all applicable local, state and federal requirements will be adhered to.

This study is to be conducted in accordance with Institutional Review Board regulations. The investigator will obtain appropriate IRB/ethics committee approval prior to initiating the study.

The study will be registered with clinicaltrials.gov.

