18.5. Study Completion

The study will be complete when all enrolled patients have completed Visit 5 or have been terminated from the study.

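### Section 18.3 ends follow-up after a severe, possibly related event even when surgery is done, so the 3-month primary outcome and scheduled exam can be lost or replaced by an early value

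*Combined protocol and SAP*

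**What the plan says.** Section 18.3 (Patient Termination) is mandatory: "A study patient will be terminated if the study patient develops any severe adverse event that may be related to the study". It then adds: "These study patients are considered to have completed the study and will not be replaced". Section 18.5 (Study Completion) treats termination as an alternative to the final visit: "The study will be complete when all enrolled patients have completed Visit 5 or have been terminated from the study". The footnote to Table 15.1 follows the same logic, with the exit form due at termination or Visit 5, whichever is earlier.

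Visit 5 is at 90 ± 20 days (Table 9.2-1). By Table 15.1 and the 3-month visit description in 9.2.4, it is the only scheduled postoperative occasion for the PROWL questionnaire and the dilated fundus exam. The 1-week and 1-month visits include neither.

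Other provisions bear on subjects who leave early or have problems:

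- Exit Procedures (the second section numbered 9.2.3) asks for the study examinations at a premature exit, as far as they can be done.
- Section 9.5 leaves stopping on health grounds to the investigator's opinion and asks for an assessment of those who leave before Visit 5.
- Section 10.1 evaluates all enrolled subjects for safety and limits efficacy analyses to eyes with uncomplicated surgery.
- Section 13.3 requires the outcome, and the resolution date where there is one, for each recorded event.
- Section 13.4 maintains medical care and follow-up. For the resulting data, the study coordinator and Medical Monitor "will determine when the data need to be documented on the CRFs".
- Section 7.3 says that "subjects who become pregnant during the study will not be discontinued but their data may be excluded from analyses of effectiveness".
- Section 9.2.2 says of subjects whose surgery was not completed successfully: "These subjects will be monitored for safety but clinical performance data may be excluded from the analysis".

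**The concern.** A rule that stops participation after a severe related event protects subjects when treatment is continuing. Here treatment is one operation on one day. For an event that begins after surgery and before Visit 5, there is no further exposure to withdraw, and termination removes only the remaining scheduled measurements.

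What is removed includes the primary outcome. A subject terminated at week 2 has no scheduled postoperative question 1, and any exit answer is given close to an incapacitating event rather than at day 70 to 110. The reason for the loss is plausibly related to satisfaction. That is an inference, since the documents give no data on it. If the answer is missing and such subjects are less satisfied than the rest, the percentage is too high. If an early exit answer is used and the subject would have been satisfied at 3 months, it is too low. A confidence interval for the percentage would show neither error.

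**Working it through.** **The plan's own figure.** Section 11 gives 46 pairs for 90% power at 5%, with a mean difference of 25 and an SD of differences of 50, so d = 25/50 = 0.5. A two-sided paired t-test (sidedness is assumed, as the plan does not state it) needs 44, and 46 gives 91.3% power. The step to enrolment fits a 10% loss: 46/0.90 = 51.1, rounded up to 52. Power is 94.3% at 52 and 91.3% at 46, so a few terminations do not threaten it. The question is bias in the primary percentage.

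**What termination removes.**

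| Item | If 18.3 is not triggered | If terminated after surgery, before Visit 5 |
|---|---|---|
| PROWL question 1 | Visit 5, day 70 to 110 (90 − 20 to 90 + 20) | At exit if feasible, otherwise none |
| Dilated fundus exam | Visit 5 | At exit if feasible, otherwise none scheduled |
| Adverse event reporting | 13.3 | 13.3 still applies |
| Medical care and follow-up | 13.4 | 13.4 and 9.5 still apply |

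**Bias per affected subject with no answer.** Let k subjects lack question 1, let p be the proportion satisfied among the rest and q the proportion who would be satisfied among the k. Take all 52 to be in the efficacy set. The upward bias is k(p − q)/52. The values of p and q are assumptions. For k = 1:

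- p = 0.90, q = 0: 0.90/52 = 1.73 points
- p = 0.95, q = 0: 0.95/52 = 1.83 points
- p = 0.90, q = 0.5: 0.40/52 = 0.77 points
- p = 0.95, q = 0.5: 0.45/52 = 0.87 points
- q = p: 0

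Check in whole subjects: 46/51 = 90.2% reported against 46/52 = 88.5% in truth, a difference of 1.7 points.

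**Opposite case.** One exit answer is taken during the event and counted as not satisfied, although the subject would have been satisfied at 3 months: 46/52 = 88.5% reported against 47/52 = 90.4%, which is 1.9 points downward.

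**How many subjects.** The documents give no rate of severe, possibly related events, so the rate r is assumed. The number affected is taken as binomial with n = 52. The expected upward bias is r(0.90 − q) × (share with no usable exit answer).

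| r | P(0 or 1 affected) | Expected bias, no exit answers (q = 0.5 to q = 0) | Expected bias, half give a usable answer (q = 0.5 to q = 0) |
|---|---|---|---|
| 0.5% | 97% | 0.20 to 0.45 | 0.10 to 0.23 |
| 1% | 90% | 0.40 to 0.90 | 0.20 to 0.45 |
| 2% | 72% | 0.80 to 1.80 | 0.40 to 0.90 |

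Subjects outside the 10.1 efficacy set do not enter the percentage, so the figures fall further to the extent that events cluster there.

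**Scale.** The 95% half-width at 90% and n = 52 is 1.96 × √(0.9 × 0.1/52) = 8.15 points, or about 8.2.

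**The case against.** The strongest reply is that the plan already covers most of this. The trigger is narrow: section 12.3.1 reserves the severe grade for incapacitating events, and the event must also be possibly related and must arise between surgery and Visit 5. Exit Procedures seeks the study examinations, and Table 15.1 lists PROWL among the assessments. Because 18.3 counts terminated subjects as completers, an exit answer can enter the 10.2 summaries, which cover eyes completing the study. Feasibility would also limit any attempt at Visit 5 in a very unwell subject. This all stands, and it makes loss of the answer possible rather than automatic. It does not supply a 3-month answer, because an exit examination is tied to the exit date.

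A reader might infer that terminated subjects disappear from safety follow-up and that adverse event durations are lost. The documents do not support that. Section 13.5 states: "The type, severity, duration and frequency of reported ocular adverse events will be tabulated". For that table, 13.3 requires onset, outcome and resolution dates. It also requires further information as it arises on serious events and on device-related ones, and 12.3.1 counts possibly related as related. The case-by-case CRF decision in 13.4 sits on top of those duties. The safety loss is mainly the fixed-date 3-month exam.

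A reader might also infer from the pregnancy and unsuccessful-surgery rules that the plan elsewhere protects the primary outcome. It does not, since both allow the efficacy data to be excluded. They show only that observation continues in other circumstances.

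**Conclusion.** The concern holds as a minor design point. As written, 18.3 and 18.5 can cost the scheduled 3-month question 1 and fundus exam, or substitute an early value, for a reason plausibly tied to outcome and with no treatment left to stop.

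The upper bound is 1.7 to 1.8 points upward per affected subject with no answer, or 1.9 points downward where an unrepresentative exit answer is used. The upward bound assumes 90% to 95% satisfaction in the rest and none among the affected, and it falls to zero if affected subjects are as satisfied as the others. At assumed event rates of 0.5% to 2%, the expected upward bias is at most 1.8 points, well inside a half-width of about 8.2. The plan sets no success threshold, so no decision turns on this.

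It would go too far to say that the reported percentage will be inflated. The direction depends on whether an exit answer is taken and how it is used, and the documents give neither an event rate nor satisfaction data for such subjects.

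**What to change.** Amend 18.3 so that a severe, possibly related event arising after surgery does not by itself end follow-up. The scheduled Visit 5 questionnaires and examination should still be obtained unless the subject withdraws consent or the investigator judges continued participation a health risk, as 9.5 already provides. Amend 18.5 to match, and align the exit-form footnote of Table 15.1.

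This reduces both biases for subjects who attend Visit 5 and are in the 10.1 efficacy set. It does not help those who fail to attend, and it does not bring eyes with complicated surgery into the efficacy analysis.

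The cost is about one sentence in each of 18.3 and 18.5 plus the footnote. Visit 5 is already scheduled, so no visit or test is added and enrolment stays at 52. The downside for the sponsor is that the reported percentage may be slightly lower.

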18.4. Study Termination

The investigator with appropriate notification may terminate the study. If, after clinical observations, the investigator feels that it may be unwise to continue the study, he may stop the study.

18.5. Study Completion

The study will be complete when all enrolled patients have completed Visit 5 or have been terminated from the study.

19. SUMMARY OF RISKS AND BENEFITS

19.1. Summary of risks

The risks with this study are similar to those for any patient receiving bilateral LASIK.⁴ There is no increased risk associated with the proposed study.

